## OFFICE OF HUMAN RESEARCH PROTECTION

reactions (defined as a 2-point increase from pre-injection pain) will be assessed and compared between the two groups. Findings indicating a statistically significant difference in the incidence and/or intensity of the flare reactions would be clinically significant and would be evidence supporting the switch of current standard practice to one corticosteroid over the other. Patients will only receive a single, standard of care, trigger finger injection on the day they present to the clinic. The next 7 days, up to two weeks if needed, of follow-up will only be a single short survey question to determine pain level.

All survey data will be collected from the patient in real-time, but the study will include a retrospective chart review to collect demographic information, injection specifics, etc.

Data to be collected: information from your existing medical records, and new information about you that is created or collected during this study, such as: history and physical information pertaining to trigger finger, nursing and staff notes pertaining to trigger finger, identifiers (name, MRN), demographic data (age/date of birth, sex, dominant hand), patient reported outcome measures scores, comorbidities (tobacco use, diabetes, fibromyalgia).

This study does not involve more than minimal risk. Risks from participation in this study include typical risks associated with a trigger finger injection: pain at injection site, soreness, etc.

The subject will receive no direct benefits. Knowledge gained from this study could help change standard of care procedures for trigger finger injections to best limit flare reactions afterward.

### Target Population & Recruitment Methods

We will recruit a minimum of 30-40 patients into each treatment group. Power analysis shows that at least 30 patients are needed to show a difference of 2-point difference between the two groups which corresponds to the minimal clinically important difference on the VAS scale assuming a standard deviation of 2.5 points. Accounting for the potential of patient data loss during follow-up surveys, we expect to need to consent and enroll 80-100 patients

#### ***Inclusion & Exclusion Criteria –***

***Inclusion:*** Adult, Single trigger injection, First time for the digit to be injected, No prior surgery on digit  
***Exclusion:*** Current oral steroid use, Rheumatoid arthritis, More than one single digit involved, Previous injection in same digit, Prior surgery on same digit, Other injections in the same clinic on the same day, Under 18, Cognitively impaired individuals, Pregnant women, Prisoners, WVU/WHUH/UHA Employees or students

#### ***Recruitment –***

Prospective subjects will be identified by the surgeon at the time of their appointment. The surgeon will inform the study coordinator of a potential participant, and the study coordinator will approach the patient for consent.

There will be n flyers or other advertisements.

### Risk & Benefit

***Risk*** – Risks from participation in this study include typical risks associated with a trigger finger injection: pain at injection site, soreness, etc.

***Benefit*** – The subject will receive no direct benefits. Knowledge gained from this study could help change standard of care procedures for trigger finger injections to best limit flare reactions afterward.

### Statistical Analysis Plan

Power analysis showed that a minimum of 30 patients are needed to show a difference of 2-point difference between the two groups which corresponds to the minimal clinically important difference on the VAS scale assuming a standard deviation of 2.5 points. We will compare the incidence, intensity, and time to flare reactions and time to resolution between the two groups using t-test and chi square tests as appropriate.

**Data Safety Monitoring** – Yes, there is a data safety monitoring plan in place for this study.

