## OFFICE OF HUMAN RESEARCH PROTECTION

**Study Design** – The two standard of care corticosteroids used for trigger finger treatment are betamethasone and methylprednisolone. Both injections are effective in treating trigger finger and the decision of which to use in treatment is currently a matter of the current practice and physician preference. There is no literature comparing the side effects, specifically flare reactions between these two treatments. Our goal through this randomized trial is to see whether there is a difference between these two corticosteroids in inducing flare reactions and if there are any differences in the peak level of pain and its duration. We will carry out a double-blinded randomized trial enrolling patients into one of the two treatment groups. The volume of the doses of steroid to be given will be standardized to 1 cc of either methylprednisolone (40 mg) or betamethasone (6 mg). We will instruct patients who meet the inclusion criteria to complete a visual analog scale (VAS) of their pain (1-10) prior to the injection, immediately after the injection, five minutes after the injection, and once a day for a minimum of 7 days after the injection. The incidence, intensity, time to peak and time to resolution of the flare reactions (defined as a 2-point increase from pre-injection pain) will be assessed and compared between the two groups. Findings indicating a statistically significant difference in the incidence and/or intensity of the flare reactions would be clinically significant and would be evidence supporting the switch of current standard practice to one corticosteroid over the other. Patients will only receive a single, standard of care, trigger finger injection on the day they present to the clinic. The next 7 days, up to two weeks if needed, of follow-up will only be a single short survey question to determine pain level.

Patients will be identified by the surgeon on the day they present to clinic, and will be recruited and consented by the study personnel. Data will be collected from the patient and stored in the REDCap server. There is not more than minimal risk involved.

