## Section II: Design

### Background & Significance

Corticosteroid injections are effective non-surgical approach to treating trigger finger (stenosing tenosynovitis) with success rates reported as high as 92% after just one injection [1]. Among their side effects is a post-injection flare of increased pain that is attributed to crystal-induced synovitis [2]. Reports of these flares in the literature have been rare. Recent evidence their incidence can be as high as 33% [3]. We feel they are a more common clinical issue than traditionally reported and it would be beneficial to control and reduce their incidence if possible.

Two common corticosteroids used for trigger finger treatment are betamethasone and methylprednisolone [4][5]. Both injections are effective in treating trigger finger and the decision of which to use in treatment is currently a matter of the current practice and physician preference. There is no literature comparing the side effects, specifically flare reactions between these two treatments. Our goal through this randomized trial is to see whether there is a difference between

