## OFFICE OF HUMAN RESEARCH PROTECTION

these two corticosteroids in inducing flare reactions and if there are any differences in the peak level of pain and their duration.

We will carry out a double-blinded randomized trial enrolling patients into one of the two treatment groups. The volume of the doses will be standardized to 1 cc of either methylprednisolone (40 mg) or betamethasone (6 mg). We will instruct patients who meet the inclusion criteria to complete a visual analog scale (VAS) of their pain (1-10) prior to the injection, during the injection and once a day for the following 7 days after the injection. We estimate that we need a minimum of 30 patients in each group to achieve a minimum of 80% power and 0.05 significance. The incidence, intensity, time to peak and time to resolution of the flare reactions (defined as a 2-point increase from pre-injection pain [3]) will be assessed and compared between the two groups. Findings indicating a statistically significant difference in the incidence and/or intensity of the flare reactions would be clinically significant and would be evidence supporting the switch of current practice to one corticosteroid over the other.

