**Study Design & Methodology**

The two standard of care corticosteroids used for trigger finger treatment are betamethasone and methylprednisolone. Both injections are effective in treating trigger finger and the decision of which to use in treatment is currently a matter of the current practice and physician preference. There is no literature comparing the side effects, specifically flare reactions between these two treatments. Our goal through this randomized trial is to see whether there is a difference between these two corticosteroids in inducing flare reactions and if there are any differences in the peak level of pain and its duration. We will carry out a double-blinded randomized trial enrolling patients into one of the two treatment groups. The volume of the doses of steroid to be given will be standardized to 1 cc of either methylprednisolone (40 mg) or betamethasone (6 mg). We will instruct patients who meet the inclusion criteria to complete a visual analog scale (VAS) of their pain (1-10) prior to the injection, immediately after the injection, five minutes after the injection, and once a day for a minimum of 7 days after the injection. The incidence, intensity, time to peak and time to resolution of the flare

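### The Statistical Analysis Plan lists time to flare where the design text commits to time to peak, and as planned either one can be tested only in patients who flare

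*Combined protocol and SAP*

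**What the plan says.** The outcome list appears in the Study Design part of the Research Summary, in Background & Significance, and in Study Design & Methodology. All three use the same four items. The Research Summary reads: "The incidence, intensity, time to peak and time to resolution of the flare reactions (defined as a 2-point increase from pre-injection pain". Each adds that these outcomes "will be assessed and compared between the two groups".

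The Statistical Analysis Plan gives a different list: "We will compare the incidence, intensity, and time to flare reactions and time to resolution between the two groups". The tests follow directly: "using t-test and chi square tests as appropriate".

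The document does not define time to peak or time to flare beyond these words. It gives no rule for patients without a flare or for flares that have not resolved when follow-up ends, and it names no time-to-event method. On how common flares are, Background & Significance says: "Recent evidence their incidence can be as high as 33" per cent. The Objectives section names flare induction, peak level of pain and duration. It names neither timing outcome.

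**The concern.** Onset and peak are different quantities. A patient's pain can cross the 2-point threshold on day 1 and reach its highest value on day 3, so the two outcomes can rank the steroids differently. An analyst who follows the Statistical Analysis Plan would test an outcome that the design text never names and would have no test for one that it names three times. With both names in the document, the choice could be made after the data are seen.

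A second issue lies beneath the wording. A patient who never flares has no time to flare, no time to peak of a flare and no time to resolution. A t-test on any of these drops that patient. Whether a patient flares is decided after randomisation and may depend on the steroid, so the patients left in the two arms need not be comparable. The document says that differences in the incidence or intensity of flares would support a change of practice. Timing results reported beside them should not be taken for randomised evidence if they are not.

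**Working it through.** **1. The lists side by side**

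| Item | Design text (three places) | Statistical Analysis Plan |
|---|---|---|
| 1 | incidence | incidence |
| 2 | intensity | intensity |
| 3 | time to peak | time to flare reactions |
| 4 | time to resolution | time to resolution |

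Three items match and one differs.

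**2. Who has a value for each timing outcome**

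The design's full phrase is "The incidence, intensity, time to peak and time to resolution of the flare reactions", so its time to peak is a property of a flare. Time to flare and time to resolution are too. Each therefore has a value only in patients who flare, and changing the name in row 3 neither adds nor removes patients.

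**3. The plan's own sample size**

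The document gives no figure for a timing outcome. Its one computed figure is at least 30 per group for a 2-point VAS difference with SD 2.5, a significance level of 0.05 and at least 80% power. The standardised difference is 2 / 2.5 = 0.8. With a two-sided test and the normal approximation:

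n = 2 × (1.96 + 0.84)² / 0.8² ≈ 24.5, so 25 per group.

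The noncentral t calculation gives 25.5, so 26 per group. With 30 per group its power is 86%, which meets the stated minimum of 80%. This calculation concerns VAS points and assumes that every patient has a value. It does not cover timing outcomes.

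**4. Size of the flare subset**

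Expected flare patients per arm = patients per arm × incidence. The numbers per arm are 30 (the stated minimum), 40 and 50 (half of the planned enrolment of 80-100, assuming equal allocation). The 33% is the background upper figure. The 10% and 20% are assumptions to show a range.

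| Patients per arm | 10% | 20% | 33% |
|---|---|---|---|
| 30 | 3 | 6 | 9.9 |
| 40 | 4 | 8 | 13.2 |
| 50 | 5 | 10 | 16.5 |

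These counts are the same for time to flare and for time to peak as the design words it.

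**5. Illustration only**

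The document gives no SD or target difference in days. If 0.8 SD is borrowed from the VAS scale, a t-test on 9.9 flare patients per arm has 39% power. That figure too is the same under either name.

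**The case against.** The best defence is that this is loose drafting. The Statistical Analysis Plan is one section of a single combined document, and the rest of that document commits plainly to comparing time to peak. The Objectives name neither timing outcome, so a secondary item is affected. This stands in part. A reader might infer that time to peak will never be analysed. The document does not support that, because the design text says it will be compared. What can be said is that the section assigning the tests leaves it out. An analyst cannot tell shorthand from intent, and the latitude in choosing tests reaches only to the two tests named.

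A reader might also infer that the change of wording is what confines the analysis to flare patients, and so lowers power from 86% with all 30 per arm to about 40%. The document does not support this either. Its own time to peak carries the same restriction, so the wording difference costs no power. The 86% would apply only to an all-patient outcome that the plan does not contain, with an effect size taken from another scale.

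Finally, the 33% is a background upper figure and not a planning assumption of this trial. The subset sizes are therefore conditional.

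**Conclusion.** The point holds and is minor. The outcome lists disagree on one item. Time to peak, stated three times in the design, has no test in the Statistical Analysis Plan, and an outcome absent from the design takes its place.

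Separately, the planned t-test on any of the timing outcomes compares a subset formed after randomisation. At 33% incidence that is about 10 of 30 patients per arm, and fewer if flares are less common. These counts assume the same incidence in both arms and no loss of data. That the subset is selected after randomisation does not depend on the incidence figure. No power figure is claimed for the timing outcomes.

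**What to change.** In the Statistical Analysis Plan, replace time to flare reactions with time to peak, so that the section tests the outcome the design states. Add that timing comparisons restricted to flare patients, including time to resolution, are descriptive. The cost is a small change of wording, with no effect on sample size or data collection.

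If a randomised comparison of timing is wanted, define time to peak pain for all randomised patients as the first day of the highest daily VAS within days 1-7, with the first day taken for ties. Days 1-7 are the daily ratings planned for every patient, whereas follow-up to two weeks is only as needed. Compare the arms with a rank-based test. The three design passages tie time to peak to flare reactions, so the Research Summary, Background & Significance, and Study Design & Methodology would need matching edits.

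The drawback is that the all-patient measure is less specific to flares, since a patient without a flare still has a highest day. Whichever form is chosen should be fixed before any outcome data are examined.

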**REFERENCES:** See References section**Objectives**

Two common corticosteroids used for trigger finger treatment are betamethasone and methylprednisolone. Both injections are effective in treating trigger finger and the decision of which to use in treatment is currently a matter of the current practice and physician preference. There is no literature comparing the side effects, specifically flare reactions between these two treatments. Our goal through this randomized trial is to see whether there is a difference between these two corticosteroids in inducing flare reactions and if there are any differences in the peak level of pain and their duration.

Findings indicating a statistically significant difference in the incidence and/or intensity of the flare reactions would be clinically significant and would be evidence supporting the switch of current practice to one corticosteroid over the other.

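### Time to resolution is compared by t-test or chi-square only, with no rule for flares unresolved or lost at the last survey

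*Combined protocol and SAP*

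**What the plan says.** The Statistical Analysis Plan is a sample size sentence followed by one analysis sentence, which compares "time to resolution between the two groups using t-test and chi square tests as appropriate". No section mentions censoring, survival methods, imputation, or a value for a flare that has not ended.

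The survey window differs by section:
- Background & Significance: "once a day for the following 7 days after the injection", with no extension.
- Research Summary, Study Design: "once a day for a minimum of 7 days after the injection". Study Design & Methodology agrees: "five minutes after the injection, and once a day for a minimum of 7 days after the injection".
- Both of those design sections also contain "The next 7 days, up to two weeks if needed, of follow-up". What triggers the extension is not stated.

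A flare is a rise of 2 points over the pain score before injection. When a flare ends is left to inference from that definition.

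Loss of survey data is expected and is met by enrolling more patients: "Accounting for the potential of patient data loss during follow-up surveys, we expect to need to consent and enroll 80-100 patients" (Target Population & Recruitment Methods).

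Duration is a stated aim. The Objectives ask "if there are any differences in the peak level of pain and their duration". The statement about changing practice rests on a "statistically significant difference in the incidence and/or intensity of the flare reactions", so duration is a supporting result.

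**The concern.** A t-test needs a number for every flare. A flare still present at the last survey, or in a patient who has stopped answering, has no observed resolution time, so the analyst must drop it or assign it a value. The plan does not say which, so the choice would be made after the data are seen.

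The choice matters because the flares without a resolution time tend to be the long ones. Dropping them lowers the mean in both arms, and lowers it most in the arm with longer flares, so the difference between arms shrinks. Enrolling more patients replaces lost numbers but does not remove this bias. An unwritten extension rule adds a further risk, because the length of follow-up could differ between patients or arms.

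**Working it through.** **The plan's own figure.** The plan has no figure for duration. Its one calculation, a minimum of 30 per group for a 2-point VAS difference with SD 2.5, does not bear on this point. For the record, 2 × (1.96 + 0.842)² × 2.5² / 2² = 24.5, so 25 per group (26 with the t distribution), and 30 meets the stated minimum of 80% power.

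**Inputs from the documents.** Last survey at day 7 or day 14. Flare incidence up to 33% (Background & Significance). Target of 30-40 per group, so 60-80 evaluable, from 80-100 enrolled. No loss rate is given. The implied range runs from 1 − 80/80 = 0% to 1 − 60/100 = 40%, and 1 − 60/80 = 25% is one point in it.

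**Assumptions.** Flare durations are exponential, one arm's mean is twice the other's, and the limit L is counted from flare onset (a later onset shortens the window).

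**Step 1: unresolved flares, no loss.** For mean m:
- share unresolved S = exp(−L/m)
- mean with unresolved flares set to L = m(1 − S)
- mean among resolved flares only = (m(1 − S) − L·S)/(1 − S)

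Example, 4 v 8 days at L = 14: S = 0.030 and 0.174, the means among resolved flares are 3.564 and 5.055, and the difference is 1.49 against a true 4.0.

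| Means (days) | True difference | Dropped, day 7 | Capped, day 7 | Dropped, day 14 | Capped, day 14 |
|---|---|---|---|---|---|
| 1.5 v 3 | 1.5 | 0.82 | 1.22 | 1.37 | 1.47 |
| 2 v 4 | 2.0 | 0.75 | 1.37 | 1.58 | 1.88 |
| 3 v 6 | 3.0 | 0.59 | 1.42 | 1.63 | 2.45 |
| 4 v 8 | 4.0 | 0.47 | 1.36 | 1.49 | 2.73 |

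The capped columns are restricted-mean differences. They are legitimate targets if named in advance, but they understate the full difference in means.

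**Step 2: survey loss added.** 4 v 8 days, L = 14, 25% lost at a uniform time, a million or more simulated flares per arm. The target is the restricted-mean difference of 2.73. In the dependent case, loss is 37.5% above and 12.5% below the arm's median duration, in both arms.

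| Handling | Loss at random | Dependent loss |
|---|---|---|
| Unresolved and lost flares dropped | 1.4 | 1.3 |
| Last survey taken as end of flare | 2.4 | 2.2 |
| Kaplan-Meier restricted mean | 2.73 | 2.66 |
| Capped mean, only patients followed to day 14 | 2.73 | 2.48 |

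The last row requires that every lost patient is left out. If patients who resolved before being lost are kept, the random-loss result falls to about 2.5.

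**Step 3: error rate and power.** 2,000 simulated trials per setting, times rounded up to whole days, 10, 13 or 16 flares per arm. With equal arms (3 v 3 days), the t-test on resolved flares rejected in 4.2% to 5.0% of trials. With 3 v 6 days and 13 flares per arm, its power was 12% (day 7) and 23% (day 14), against 36% and 40% for log-rank with censoring.

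**Step 4: what a log-rank test can detect.** Power = Φ(√(d/4) × ln 2 − 1.96) for d resolved flares at an assumed hazard ratio of 2:
- d = 20 (33% of 60): 34%
- d = 26 (33% of 80): 42%
- d = 33 (33% of 100 enrolled): 51%

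These figures take every flare as resolving on study. Power of 80% needs d = 4 × (1.96 + 0.842)² / (ln 2)² = about 65.

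**The case against.** The strongest case is that the fault is a missing rule, not a wrong test. A reader might infer that t-test and chi-square cannot serve here at all. The documents do not support that. If loss is unrelated to the course of the flare, which Kaplan-Meier also assumes, a t-test on capped times or a chi-square on the share resolved, in patients followed to a set day, is unbiased (2.73 in Step 2). This stands. The reasons to prefer Kaplan-Meier are narrower: it keeps patients with partial follow-up, and it was less sensitive to dependent loss in the case simulated (2.66 v 2.48).

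The day-7 figures may also be too severe. Only Background & Significance stops at day 7, and the natural reading of the extension is that surveys continue while pain persists. With short flares all followed to day 14, little is lost. This stands as a limit on size, but no written trigger ensures that follow-up.

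Finally, a flare's end can be inferred from its definition. That is fair: the definition is implicit rather than absent, and one sentence would settle it. The phrase in the plan that leaves the test to judgement does not answer the concern, because it chooses between two tests and gives no rule for times that were not observed.

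**Conclusion.** The point holds. The plan does not say how unresolved or lost flares enter the comparison of time to resolution, and its survey windows do not agree. Analysing only observed resolution times would understate duration and dilute the difference between arms.

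The size rests on assumed exponential durations, because the documents give none. It is small if flares are short and every unresolved flare is followed to day 14 (1.4 of a true 1.5 days at 1.5 v 3). It is larger with longer flares, a day-7 stop or survey loss (0.5 to 1.5 of a true 4.0 days at 4 v 8 before any loss).

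Three stronger readings are not supported:
- That the sponsor plans to drop unresolved flares. The plan is silent.
- That the comparison would produce false positives. With equal arms the error rate stayed near 5%; this could change if loss differs by arm.
- That the practice-change conclusion falls. It rests on incidence and intensity.

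The change should be made, but it concerns a supporting result.

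**What to change.** Amend the Statistical Analysis Plan as follows.

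1. Define resolution as the first day on which VAS is less than 2 points above the pre-injection score, timed from the first flare day. State how missed days within a flare are handled, and whether the readings immediately and five minutes after injection can start one.
2. Reconcile the survey window in Background & Significance with the two study design sections, and apply one written extension rule in both arms.
3. Censor at the last completed survey. Compare flare patients by Kaplan-Meier with log-rank, or by a Kaplan-Meier restricted mean to one common day inside the reconciled window. State the assumption that loss is unrelated to flare course.
4. Flare patients are a subset formed after randomisation. If a supporting count in all randomised patients of days at least 2 points above baseline is added (0 if no flare), give it a rule for missed days.
5. Label the duration comparison secondary or exploratory, given the power in Step 4.

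The cost is SAP wording and standard software. No new data are needed if the existing two-week option is used under a written rule. The downside is that the result is a curve, a median or a restricted mean rather than a simple difference in means. The gain is a less biased estimate fixed in advance, not an adequately powered test.

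### Pre-injection pain is recorded for every patient, but the planned t-test and chi-square test do not adjust for it, so precision available from data already collected is given up.

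*Combined protocol and SAP*

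**What the plan says.** Study Design & Methodology has each eligible patient "complete a visual analog scale (VAS) of their pain (1-10) prior to the injection", with further scores after it. The Objectives ask whether the steroids differ in causing flares and "if there are any differences in the peak level of pain and their duration". A flare is "defined as a 2-point increase from pre-injection pain".

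The analysis is set out in one sentence of the Statistical Analysis Plan, which ends "time to resolution between the two groups using t-test and chi square tests as appropriate". No ANCOVA, regression, stratified test or covariate is named anywhere in the document.

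On sample size, Background & Significance says "We estimate that we need a minimum of 30 patients in each group to achieve a minimum of 80% power and 0.05 significance". Target Population & Recruitment Methods ties the 2-point difference to the "minimal clinically important difference on the VAS scale assuming a standard deviation of 2.5 points". It sets recruitment at 30 to 40 or more per group, with 80 to 100 enrolled to cover data loss. Neither place says whether 2.5 is the SD of a raw score or of change from baseline.

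**The concern.** The pre-injection score is likely to predict later pain on the same scale. An unadjusted comparison leaves in the estimate both the variance that this score explains and any chance difference in it between arms. Baseline does enter the flare definition, but subtracting it or applying a threshold to it is not covariate adjustment.

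The plan also does not say whether intensity means the peak score or the rise above baseline. The t-test's power depends heavily on which is used, whereas ANCOVA gives the same treatment comparison for both. The stakes are a wider interval than necessary and a result more exposed to chance imbalance, in a trial whose findings are meant to support a change of practice.

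A related limit concerns incidence. On a 1-10 scale, a patient who starts at 9 or 10 cannot rise by 2 points and so cannot count as a flare.

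**Working it through.** **Inputs from the documents.** Difference 2 points; SD 2.5; significance level 0.05 (taken as two-sided); at least 80% power; 30 per group. An equal split of 80 to 100 enrolled gives 40 to 50 per group before losses.

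**Assumed.** Correlation r between pre-injection and peak score, from 0.2 to 0.6; equal SDs before and after injection; 1:1 allocation.

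**The plan's own figure.** Normal approximation: n = 2 × (1.96 + 0.842)² × 2.5² / 2² = 24.5, so 25 per group. The t distribution gives 26. Thirty per group is therefore conservative for 80%: noncentral-t power is 86.1% at 30, 94.2% at 40 and 97.7% at 50.

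**Case A: 2.5 is the raw-score SD.** The ANCOVA residual SD is 2.5 × √(1 − r²), with 2n − 3 degrees of freedom. The SD of change is 2.5 × √(2(1 − r)). At 30 per group:

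| r | ANCOVA SD | Power, raw t-test | Power, ANCOVA | Power, change t-test | ANCOVA 95% half-width |
|---|---|---|---|---|---|
| 0.2 | 2.45 | 86.1% | 87.5% | 67.3% | 1.27 |
| 0.3 | 2.38 | 86.1% | 89.1% | 73.1% | 1.23 |
| 0.5 | 2.17 | 86.1% | 94.0% | 86.1% | 1.12 |
| 0.6 | 2.00 | 86.1% | 96.8% | 92.6% | 1.03 |

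The unadjusted raw half-width is 2.00 × 2.5 × √(2/30) = 1.29. At 40 per group, ANCOVA power is 95.0%, 95.9%, 98.3% and 99.3% against 94.2%. At 50 it is 98.1%, 98.6%, 99.6% and 99.9% against 97.7%.

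**Allowance for chance imbalance.** Multiplying the ANCOVA variance by 1 + 1/(2n − 4) gives power at 30 per group of about 87%, 89%, 94% and 96.5% at r = 0.2, 0.3, 0.5 and 0.6. It is 85.9% at r = 0.1 and 85.5% at r = 0, against 86.1% unadjusted.

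**Effect of the bounded scale.** A simulation rounded scores and capped them to 1-10 (assumed means of 5, 30 per group). Power was 85% for the t-test and 86%, 87%, 92% and 95% for ANCOVA at r = 0.2, 0.3, 0.5 and 0.6. Type I error was 4.9 to 5.1% for both.

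**Case B: 2.5 is the SD of change.** The ANCOVA SD is 2.5 × √((1 + r)/2). At 30 per group, power is 97.6%, 96.5%, 94.0% and 92.6% at r = 0.2, 0.3, 0.5 and 0.6, against 86.1% for the change t-test.

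**Chance baseline difference.** With an assumed baseline SD of 2.5, its standard error at 30 per group is 2.5 × √(2/30) = 0.645. The probability of a gap of 1 point or more is 12% (7% at 40 per group). Each point of gap moves the unadjusted raw difference by r points.

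**Flare incidence.** A simulation at 30 per group (assumed baseline mean 4, SD 2.5, scale 1-10) compared the variance of the adjusted and unadjusted risk differences. The ratio was 0.81-0.85 at r = 0.2, 0.89-0.94 at r = 0.5 and 0.95-0.98 at r = 0.7.

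**Ceiling.** 9 + 2 = 11 exceeds the top of the scale, while 8 + 2 = 10 does not. No baseline distribution is given, so the number of patients affected cannot be sized.

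**The case against.** The strongest reply is that this is a refinement of a sound plan. The unadjusted tests are valid, and the raw-score t-test exceeds the 80% target at the minimum group size. Thirty is the floor: at 40 per group and r of 0.2 to 0.3, ANCOVA adds only 1 to 2 percentage points of power. Background & Significance attributes flares to crystal-induced synovitis, which need not track presenting pain, so a low r is possible. All of this stands, and it keeps the point at the level of a recommended improvement.

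The 73% figure is conditional. It requires that 2.5 is a raw-score SD and that change is what gets tested, and it applies at 30 per group. At r = 0.3 the change t-test has 85% power at 40 per group and 92% at 50. That is fair, but the plan's wording does not exclude this analysis, and ANCOVA removes the dependence on the choice.

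Intensity might also mean severity among flare cases only, and then none of these power figures apply. The Objectives' reference to peak pain supports the all-patient reading, but the SAP should say so. Finally, covariate adjustment does not remove the ceiling problem, and no gain has been computed for time to flare or time to resolution.

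**Conclusion.** The concern holds as a matter of efficiency. The baseline score is collected and neither planned test uses it as a covariate. At 30 per group with a raw-score SD of 2.5, adjustment raises power for 2 points from 86% to between 87% and 97%. It narrows the 95% interval half-width by 0.02 to 0.26 points as assumed r goes from 0.2 to 0.6. At r of 0.1 or less there is no useful gain, and at 50 per group the gain is about 2 points of power at most. Apart from one degree of freedom and a small allowance for chance imbalance, ANCOVA is at least as precise as the t-test whether 2.5 is a raw-score or a change SD. These sizes rest on the assumed r and on equal SDs before and after injection. The trial does not fail without the change, but it should be made.

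**What to change.** Amend the Statistical Analysis Plan before unblinding:

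- **Intensity.** Define it as peak post-injection VAS in all patients, over a stated window. Replace the t-test with ANCOVA of that peak on arm and pre-injection VAS, reporting the adjusted difference with its 95% interval.
- **Standard deviation.** State whether 2.5 refers to a raw score or to change.
- **Flare incidence.** Use logistic regression on arm and pre-injection VAS, reported as a standardised risk difference with 95% interval, because a baseline-adjusted odds ratio answers a different question. Keep the chi-square test as supportive.
- **Ceiling.** Report the number per arm starting at 9 or 10. Add a sensitivity analysis of incidence in patients starting at 8 or below.

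The cost is SAP wording and one degree of freedom, with no extra patients, visits or measurements. If r is 0, power at 30 per group falls from about 86.1% to 85.5%.
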